7.1.3.1 Serum-specific IgE

Blood samples will be collected at screening (Visit 1) for determination of serum-specific IgE against ragweed (*Ambrosia artemisiifolia*), other weeds (dependent upon region), grasses (dependent upon region), oak and other trees (dependent upon region), cat, dog, alternaira, cladosporium, dust mites, mugwort, and other allergens considered clinically relevant for a particular locale.

A subject must have a specific IgE against *Ambrosia artemisiifolia* of ≥ 0.7 kU/L at screening to be included in the trial.

7.1.3.2 Laboratory Safety Evaluations (Hematology, Chemistry and Urinalysis)

Laboratory tests for hematology, chemistry and urinalysis are specified in [Table 6](#).

Laboratory evaluations will be performed at a central laboratory chosen by the Sponsor. If all of the laboratory values are within the normal reference range at Screening Visit 1, the subject may continue to be evaluated for study entry. If one or more values fall outside of the normal range, the investigator may either exclude the subject from the study or investigate further to determine clinical relevance (Section 12.5). The investigation will include a careful evaluation of the potential subject's complete medical history and current physical examination in the context of the abnormal laboratory value(s). If the investigator does not identify any medical condition or disease that could results in the observed laboratory abnormality, the abnormal laboratory value may be considered not clinically relevant by the investigator and will be documented as such on the laboratory results form. Any questionable laboratory results should be reviewed with the Sponsor prior to randomization (Section 12.5). Repeat laboratory testing, at the discretion of the investigator and/or Sponsor, is permitted and should be indicated as such. If there is any clinical uncertainty regarding the significance of an abnormal value(s), the subject will be excluded from the study.

All laboratory results must be found clinically acceptable to the investigator, and Sponsor, where appropriate, prior to study medication administration.

Table 6 Laboratory Tests

Hematology	Chemistry	Urinalysis	Other
Hematocrit	Albumin	Blood	
Hemoglobin	Alkaline phosphatase	Glucose	Serum β -human chorionic gonadotropin (β -hCG) ^a
Platelet count	Alanine aminotransferase (ALT)	Protein	
WBC (total and differential)	Aspartate aminotransferase (AST)	Specific gravity	
	Bicarbonate	Microscopic exam, if abnormal results are noted	
	Blood Urea Nitrogen		
	Calcium		
	Chloride		

Hematology	Chemistry	Urinalysis	Other
	Creatinine		
	Glucose		
	Phosphorus		
	Potassium		
	Sodium		
	Total Bilirubin		
	Direct Bilirubin, if total bilirubin is elevated above the upper limit of normal		
	Total protein		
^a Only performed if urine pregnancy test is positive.			

7.1.3.3 Urine Pregnancy Test

A female subject of childbearing potential must have a negative urine pregnancy test at Visits 1 and 2 to be eligible to participate in the study. A positive urine pregnancy test should be followed up with a serum pregnancy test (β -hCG). Pregnancy tests should be repeated as per the Trial Flow Chart (Section 6.0).

7.1.3.4 Pharmacodynamic Evaluations

Blood samples for the immunologic assessment will be collected for a subset of subjects at selected sites per the study flow chart (Section 6.0). The serum samples for analyses of specific IgE and IgG₄ will be submitted to ALK-Abelló for measurement.

7.1.3.5 Future Biomedical Research

The following specimens are to be obtained as part of Future Biomedical Research:

- Saliva for future research,
- Leftover main study serum from immunologic samples (IgE, IgG₄) stored for future research.

7.1.4 Other Procedures

7.1.4.1 Withdrawal/Discontinuation

When a subject discontinues/withdraws from participation in the trial, all applicable activities scheduled for the final trial visit should be performed at the time of discontinuation. Any adverse events which are present at the time of discontinuation/withdrawal should be followed in accordance with the safety requirements outlined in Section 7.2 - Assessing and Recording Adverse Events.

7.1.4.1.1 Withdrawal From Future Biomedical Research

Subjects may withdraw their consent for Future Biomedical Research and have their specimens and all derivatives destroyed. Subjects may withdraw consent at any time by contacting the principal investigator for the main trial. If medical records for the main trial

are still available, the investigator will contact the Sponsor using the designated mailbox ([contact]), and a form will be provided by the Sponsor to obtain appropriate information to complete specimen withdrawal. Subsequently, the subject's specimens will be removed from the biorepository and be destroyed. A letter will be sent from the Sponsor to the investigator confirming the destruction. It is the responsibility of the investigator to inform the subject of completion of destruction. Any analyses in progress at the time of request for destruction or already performed prior to the request being received by the Sponsor will continue to be used as part of the overall research trial data and results. No new analyses would be generated after the request is received.

In the event that the medical records for the main trial are no longer available (e.g., if the investigator is no longer required by regulatory authorities to retain the main trial records) or the specimens have been completely anonymized, there will no longer be a link between the subject's personal information and their specimens. In this situation, the request for specimen destruction cannot be processed.

7.1.4.2 Blinding/Unblinding

When the investigator or sub-investigator needs to identify the drug used by a subject and the dosage administered in case of emergency e.g., the occurrence of serious adverse experiences, he/she will contact the emergency unblinding call center by telephone and make a request for emergency unblinding. As requested by the investigator or sub-investigator the emergency unblinding call center will provide the information to him/her promptly and report unblinding to the sponsor. The emergency unblinding call center will make a record promptly however, the investigator or sub-investigator must enter the intensity of the adverse experiences observed, their relation to study drug, the reason thereof, etc., in the medical chart etc., before unblinding is performed.

Additionally, the investigator must go into the IVRS system and perform the unblind in the IVRS system to update drug disposition. In the event that the emergency unblinding call center is not available for a given site in this trial, IVRS/IWRS should be used for emergency unblinding in the event that this is required for subject safety.

In the event that unblinding has occurred, the circumstances around the unblinding (e.g., date and reason) must be documented promptly, and the Sponsor Clinical Director notified as soon as possible. Only the principal investigator or delegate and the respective subject's code should be unblinded. Trial site personnel and Sponsor personnel directly associated with the conduct of the trial should not be unblinded.

7.1.4.3 Calibration of Critical Equipment

The investigator or qualified designee has the responsibility to ensure that any critical device or instrument used for a clinical evaluation/test during a clinical trial that provides important information about inclusion/exclusion criteria and/or safety or efficacy parameters shall be suitably calibrated and maintained to ensure that the data obtained is reliable and/or reproducible. Documentation of equipment calibration must be retained as source documentation at the trial site.

Critical Equipment for this trial includes:

- Spirometer

The spirometer must be calibrated according to American Thoracic Society guidelines. Calibration checks should be performed (i.e., with a 3-liter syringe) at a minimum of each day that a trial subject performs a spirometry assessment. The calibration check records should be printed and kept in a reviewable log. It is preferred that the calibration syringe used to check calibration of the spirometer also be subjected to a validated calibration according to the manufacturer's specifications.

7.1.5 Visit Requirements

Visit requirements are outlined in Section 6.0 - Trial Flow Chart. Specific procedure-related details are provided above in Section 7.1 - Trial Procedures.

7.2 Assessing and Recording Adverse Events

An adverse event is defined as any untoward medical occurrence in a patient or clinical investigation subject administered a pharmaceutical product and which does not necessarily have to have a causal relationship with this treatment. An adverse event can therefore be any unfavourable and unintended sign (including an abnormal laboratory finding, for example), symptom, or disease temporally associated with the use of a medicinal product or protocol-specified procedure, whether or not considered related to the medicinal product or protocol-specified procedure. Any worsening (i.e., any clinically significant adverse change in frequency and/or intensity) of a preexisting condition that is temporally associated with the use of the Sponsor's product, is also an adverse event.

Changes resulting from normal growth and development that do not vary significantly in frequency or severity from expected levels are not to be considered adverse events. Examples of this may include, but are not limited to, teething, typical crying in infants and children and onset of menses or menopause occurring at a physiologically appropriate time.

Sponsor's product includes any pharmaceutical product, biological product, device, diagnostic agent or protocol-specified procedure, whether investigational (including placebo or active comparator medication) or marketed, manufactured by, licensed by, provided by or distributed by the Sponsor for human use.

Adverse events may occur during clinical trials, or as prescribed in clinical practice, from overdose (whether accidental or intentional), from abuse and from withdrawal.

All adverse events that occur after the consent form is signed but before randomization must be reported by the investigator if they cause the subject to be excluded from the trial, or are the result of a protocol-specified intervention, including but not limited to washout or discontinuation of usual therapy, diet, placebo treatment or a procedure. From the time of randomization through 14 days following cessation of treatment, all adverse events must be reported by the investigator. Such events will be recorded at each examination on the Adverse Event case report forms/worksheets. The reporting timeframe for adverse events meeting any serious criteria is described in Section 7.2.3.1. The investigator will make every attempt to follow all subjects with non-serious adverse events for outcome.

Electronic reporting procedures can be found in the EDC data entry guidelines. Paper reporting procedures can be found in the Investigator Trial File Binder (or equivalent).

7.2.1 Definition of an Overdose for This Protocol and Reporting of Overdose to the Sponsor

In this trial, an overdose is any dose higher than the dose specified in Section 5.2 of this protocol.

If an adverse event(s) is associated with (“results from”) the overdose of Sponsor's product or vaccine, the adverse event(s) is reported as a serious adverse event, even if no other seriousness criteria are met.

If a dose of Sponsor's product or vaccine meeting the protocol definition of overdose is taken without any associated clinical symptoms or abnormal laboratory results, the overdose is reported as a non-serious Event of Clinical Interest (ECI), using the terminology “accidental or intentional overdose without adverse effect.”

All reports of overdose with and without an adverse event must be reported by the investigator within 24 hours to the Sponsor either by electronic media or paper. Electronic reporting procedures can be found in the EDC data entry guidelines. Paper reporting procedures can be found in the Investigator Trial File Binder (or equivalent).

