1.0 TRIAL SUMMARY

Abbreviated Title	MK-3641 Ragweed Pediatric Allergic Rhinoconjunctivitis Efficacy/Safety Study
Trial Phase	Phase III
Clinical Indication	Ragweed pollen-induced rhinoconjunctivitis with or without asthma
Trial Type	Interventional
Type of control	Placebo
Route of administration	Sublingual
Trial Blinding	Double-blind
Treatment Groups	MK-3641 (12 Amb a 1-U); Placebo
Number of trial subjects	Approximately 1000 subjects will be enrolled.
Estimated duration of trial	The sponsor estimates that the trial will require approximately 3.5 years from the time the first subject signs the informed consent until the last subject's last visit.
Duration of Participation	Each subject will participate in the trial for up to approximately 20 months from the time the subject signs the Informed Consent Form (ICF) through the final contact. After a screening phase of up to 12 months, each subject will be receiving assigned treatment for up to 28 weeks. After the end of treatment, each subject will be followed for 14 days.
Randomization Ratio	1:1

A list of abbreviations used in this document can be found in Section 12.13.

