2.0 TRIAL DESIGN

2.1 Trial Design

This is a randomized, placebo-controlled, parallel-group, multi-site, double-blind trial of MK-3641 in children with ragweed pollen-induced allergic rhinitis/rhinoconjunctivitis, with or without asthma, to be conducted in conformance with Good Clinical Practices. Approximately 1000 children ages 5 to 17 years will be randomized in a 1:1 ratio to receive either MK-3641, at a dose of 12 Amb a 1-U, or placebo once daily for a total of approximately 20 to 28 weeks. Subjects will be stratified by age to ensure an adequate number of subjects at younger ages are included. Subjects will also be stratified by asthma status. There may be multiple separate cohorts (approximately 2 to 3) recruited over consecutive ragweed seasons to complete the enrollment goal.

The trial consists of a screening period and a treatment period, which includes pre-seasonal and co-seasonal treatment. The screening period may last for up to approximately 12 months prior to randomization. Once randomized, subjects are treated with a minimum of approximately 12 weeks (up to approximately 20 weeks) of pre-seasonal treatment and approximately 8 weeks of co-seasonal treatment. There will be at least 7 clinic visits:

screening (Visit 1), randomization (Visit 2), Off-season (Visit 3), Off-season (Visit 4), Pre-season (Visit 6), In-season (Visit 7), and End-of-season (Visit 8 or Discontinuation Visit); Off-season (Visit 5) is only required if the time between Visit 4 and 6 is longer than 6-8 weeks. Subject compliance with study drug administration, rescue medication use, and daily e-diary completion will be monitored. Compliance issues will prompt site retraining of subject/parent/guardian via telephone contacts as necessary. The End-of-season visit will be scheduled approximately 1 week after the end of the ragweed season. A final telephone contact will occur approximately 14 days after the End-of-season (or discontinuation) visit for the safety follow-up. Unscheduled visits are also permitted, if needed. The trial diagram is outlined in Section 2.2.

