DNA = deoxyribonucleic acid; e-diary = electronic diary; FBR = future biomedical research; FEV ₁ = forced expiratory volume in 1 second; IgE = immunoglobulin E; IgG ₄ = immunoglobulin G ₄ ; IVRS/IWRS = Interactive Voice/Web Response System; PFT = pulmonary function test; RS = ragweed season; SLIT= sublingual immunotherapy; US = United States. ^{a.} All subjects are to complete Visit 4 midway between Visit 3 and Visit 6, but not more than 6 to 8 weeks after Visit 3. If time between Visits 4 & 6 is > 6 to 8 weeks, then subject should be scheduled to return for Visit 5 approximately midway between Visits 4 and 6; study drug is not dispensed at Visit 5 (see Section 9.2 for the visits when study drug is dispensed). ^{b.} During the first season of screening, subjects may be in screening up to approximately 9 months (-39 to -1 week). During subsequent season(s) of screening, subjects may be in screening up to approximately 12 months (-52 to -1 week). ^{c.} Visit 3 should be scheduled on Day 28 (+7 days) to allow the subject to complete the SLIT Report Card for ~28 days. ^{d.} It is preferable that Visit 7 be scheduled approximately 3 weeks after the start of the ragweed season. ^{e.} Informed consent/assent must be obtained before any trial-related procedures are performed. ^{f.} Informed consent for future biomedical research samples (optional) must be obtained before the saliva for DNA sample. ^{g.} Update Subject Identification Card with randomization number. ^{h.} The Anaphylaxis Emergency Action Plan can be modified outside the US to meet local standards for the use (or type) of epinephrine dispensed, and for calls to 911 or alternative local emergency services.								

Trial Period:	Screening	Treatment						Post-treatment
Visit Number:	1	2	3	4/5 ^a	6	7	8	--
Visit Title:	Screening	Randomization	Off-Season	Off-Season	Pre-Season	In-Season	End-of-Season/ Discontinuation	Telephone/ Follow-up
Scheduled Day/Week:	Weeks -52 to -1 ^b	Day 1	Week 4 ^c	Midway between Visits 3 & 6	~2 weeks before start of RS	~3 weeks after start of RS ^d	~1 week after end of RS	Post 14 days
Scheduling Window (Days):	-	-	+7 days		± 7 days		± 7 days	± 5 days

- ^{i.} Self-injectable epinephrine is provided only in those countries where it is a regulatory requirement.
- ^{j.} Albuterol/salbutamol should also be dispensed to subjects diagnosed with asthma during the trial as needed.

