7.1.1.10 Dispense Comment Card

The investigator or designee will train the subject/parent/guardian on the use of the Comment Card prior to dispensing study medication to the subject at randomization (Visit 2). The Comment Card will be dispensed at Visits 2 through 7, reviewed at the next scheduled clinic visit (Visits 3 through 8), and stored in the subject's source document file. Any AE data from the Comment Card will be entered into the eCRF with appropriate assessments made by the investigator. Any concomitant therapy data from the Comment Card will be entered as appropriate into the eCRF.

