7.2.3 Immediate Reporting of Adverse Events to the Sponsor

7.2.3.1 Serious Adverse Events

A serious adverse event is any adverse event occurring at any dose or during any use of Sponsor's product that:

- Results in death;
- Is life threatening;
- Results in persistent or significant disability/incapacity;
- Results in or prolongs an existing inpatient hospitalization;
- Is a congenital anomaly/birth defect;
- Is an other important medical event

Note: In addition to the above criteria, adverse events meeting either of the below criteria, although not serious per ICH definition, are reportable to the Sponsor in the same timeframe as SAEs to meet certain local requirements. Therefore, these events are considered serious by the Sponsor for collection purposes.

- Is a cancer;
- Is associated with an overdose.

Refer to [Table 7](#) for additional details regarding each of the above criteria.

For the time period beginning when the consent form is signed until randomization, any serious adverse event, or follow up to a serious adverse event, including death due to any cause, that occurs to any subject must be reported within 24 hours to the Sponsor if it causes the subject to be excluded from the trial, or is the result of a protocol-specified intervention, including but not limited to washout or discontinuation of usual therapy, diet, placebo treatment or a procedure.

For the time period beginning at randomization through 14 days following cessation of treatment, any serious adverse event, or follow up to a serious adverse event, including death due to any cause, whether or not related to the Sponsor's product, must be reported within 24 hours to the Sponsor either by electronic media or paper. Electronic reporting procedures can be found in the EDC data entry guidelines. Paper reporting procedures can be found in the Investigator Trial File Binder (or equivalent).

Additionally, any serious adverse event, considered by an investigator who is a qualified physician to be related to the Sponsor's product that is brought to the attention of the investigator at any time outside of the time period specified in the previous paragraph also must be reported immediately to the Sponsor.

All subjects with serious adverse events must be followed up for outcome.

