7.2.3.2 Events of Clinical Interest

Selected non-serious and serious adverse events are also known as Events of Clinical Interest (ECI) and must be reported to the Sponsor.

For the time period beginning when the consent form is signed until randomization, any ECI, or follow up to an ECI, that occurs to any subject must be reported within 24 hours to the Sponsor if it causes the subject to be excluded from the trial, or is the result of a protocol-specified intervention, including but not limited to washout or discontinuation of usual therapy, diet, placebo treatment or a procedure.

For the time period beginning at randomization through 14 days following cessation of treatment, any ECI, or follow up to an ECI, whether or not related to the Sponsor's product, must be reported within 24 hours to the Sponsor, either by electronic media or paper. Electronic reporting procedures can be found in the EDC data entry guidelines. Paper reporting procedures can be found in the Investigator Trial File Binder (or equivalent).

Events of clinical interest for this trial include:

1. an overdose of Sponsor's product, as defined in Section 7.2.1 - Definition of an Overdose for This Protocol and Reporting of Overdose to the Sponsor, that is not associated with clinical symptoms or abnormal laboratory results.
2. an elevated AST or ALT lab value that is greater than or equal to 3X the upper limit of normal and an elevated total bilirubin lab value that is greater than or equal to 2X the upper limit of normal and, at the same time, an alkaline phosphatase lab value that is less than 2X the upper limit of normal, as determined by way of protocol-specified laboratory testing or unscheduled laboratory testing.*

*Note: These criteria are based upon available regulatory guidance documents. The purpose of the criteria is to specify a threshold of abnormal hepatic tests that may require an additional evaluation for an underlying etiology. The trial site guidance for assessment and follow up of these criteria can be found in the Investigator Trial File Binder (or equivalent).

3. Anaphylactic reactions, anaphylaxis and/or systemic allergic reactions.
4. Events treated with epinephrine.
5. Severe local swelling or edema of the mouth and/or throat.
6. Severe drug-related asthma exacerbations.
7. Eosinophilic esophagitis.

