8.2.4 Analysis Populations

8.2.4.1 Efficacy Analysis Populations

The Full Analysis Set (FAS) population will serve as the primary population for the analysis of efficacy data in this study. The FAS population consists of all randomized subjects who receive at least one dose of study treatment. Subjects will be analyzed according to the treatment group to which they are randomized.

A supportive analysis using the Per-Protocol (PP) population will be performed for the primary efficacy endpoint. The PP population excludes subjects due to important deviations from the protocol that may substantially affect the results of the primary efficacy endpoints. The major protocol violations that would lead to exclusion of a subject or a data point are described below:

- Subjects with asthma requiring prescribed high daily doses of inhaled corticosteroids (as defined in the protocol);
- Subjects with chronic sinusitis during the previous 2 years;
- Subjects treated with immunotherapy within 5 years prior to screening;
- Subjects unable to meet medication washout requirements;
- Subjects randomized in the study more than once;
- Subjects who participated in the same study at another site;
- Subjects with pre-seasonal duration of treatment exposure < 56 Days;
- Subjects with a negative skin prick test response to ragweed;
- Subjects with specific IgE to ragweed < 0.7 kU/L;

- Subjects with overall treatment compliance < 75% between Visit 2 and Visit 8;
- Subjects who took prohibited medications as defined in the protocol, with the exception of antihistamines. Subjects who have taken antihistamines (other than sponsor provided rescue medications) will be considered protocol violators if they have taken the medication for 2 or more consecutive days between Visit 6 and Visit 8;
- Subjects who had their blinded treatment randomization code broken.

Analyses related to SABA use and nocturnal awakening will be based on subjects with asthma in the FAS population.

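### The ± 5-day window on the only post-treatment call can leave up to 5 days of the 14-day adverse-event period without active questioning

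*Protocol*

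**What the plan says.** Three parts of Protocol Section 7.2 use the same end point for safety reporting.

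- Adverse events (Section 7.2): "From the time of randomization through 14 days following cessation of treatment, all adverse events must be reported by the investigator".
- Serious adverse events (Section 7.2.3.1): "For the time period beginning at randomization through 14 days following cessation of treatment, any serious adverse event", whether or not related.
- Events of clinical interest (Section 7.2.3.2): "For the time period beginning at randomization through 14 days following cessation of treatment, any ECI", again whether or not related.

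Section 1.0 gives follow-up the same length: "After the end of treatment, each subject will be followed for 14 days". It also defines participation as running through the final contact.

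That contact is described in Section 2.1: "A final telephone contact will occur approximately 14 days after the End-of-season (or discontinuation) visit for the safety follow-up". The flow chart in Section 6.0 lists it in the Telephone/Follow-up column at 14 days, with a scheduling window of ± 5 days, and marks adverse-event monitoring there. Under Section 7.1.1.10 and the flow chart, the Comment Card is last handed out at Visit 7 and last reviewed at Visit 8.

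**The concern.** The reporting period and the contact meant to close it do not match. The period runs a full 14 days from the end of treatment, but the call may be made up to 5 days before its target. Nothing in the documents requires the call on or after Day 14, or a second contact after an early one. With no Comment Card issued at Visit 8, the call is the only planned collection of adverse events after that visit.

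At stake is whether the schedule delivers the 14-day follow-up that Section 1.0 states. A late event that a family does not think to mention could be missed. Section 4.2.1 describes this as the first trial of the product in children aged 5 to 17 years, and overall safety is a secondary objective (Section 3.2), so the stated follow-up should be one that the schedule guarantees.

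**Working it through.** This is day-counting; no power or error-rate formula is involved.

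**Inputs**

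- Reporting period after the last dose: 14 days (Sections 7.2, 7.2.3.1, 7.2.3.2).
- Call target: 14 days after Visit 8 or the discontinuation visit (Sections 2.1 and 6.0).
- Call window: ± 5 days (Section 6.0).
- L, the number of days from last dose to Visit 8: not fixed by the documents, so it is varied below.

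**Permitted call days.** 14 − 5 = 9 and 14 + 5 = 19, so the call day C after Visit 8 can be any of Days 9 to 19.

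**Gap.** Days of the reporting period left after the call = max(0, 14 − (L + C)).

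*Last dose on the day of Visit 8 (L = 0):*

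| Call day C | 9 | 10 | 11 | 12 | 13 | 14 to 19 |
|---|---|---|---|---|---|---|
| Gap (days) | 5 | 4 | 3 | 2 | 1 | 0 |

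*Earliest permitted call (C = 9):*

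| L (days) | 0 | 1 | 2 | 3 | 4 | 5 or more |
|---|---|---|---|---|---|---|
| Gap (days) | 5 | 4 | 3 | 2 | 1 | 0 |

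**Relative size of the worst case.** 5/14 = 36% of the post-treatment period. Against total observation, with 20 to 28 weeks of treatment plus 14 days, it is 5/(20 × 7 + 14) = 5/154 = 3.2% down to 5/(28 × 7 + 14) = 5/210 = 2.4%.

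**With a window of +5 days.** C runs from 14 to 19, so L + C is at least 14 and the gap is 0 for every L.

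**Which L is plausible.** Several features point to dosing up to Visit 8:

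- The flow chart places Visit 8 in the treatment period, with study-drug collection and a compliance check.
- Section 8.2.4.1 measures compliance up to that visit: "Subjects with overall treatment compliance < 75% between Visit 2 and Visit 8".
- Section 1.0 counts the 14 days from the end of treatment while Section 2.1 counts them from Visit 8. The two agree if treatment ends at Visit 8.
- No section tells families to stop when the season ends.

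**The case against.** The strongest objection is to L = 0. Section 4.2.2.2 describes treatment continuing through the ragweed season, and Visit 8 falls about 1 week after the season ends. If dosing stops at season end and Visit 8 is on target, L is about 7 and the gap is zero for every permitted call. The compliance criterion is an overall percentage and does not prove a dose on the final day. Section 8.2.10 counts to a last scheduled treatment day without equating it to Visit 8. At a discontinuation visit the last dose may also be days earlier. This stands as a limit: the gap is conditional on the last-dose day. It does not remove the point. Visit 8 itself has a ± 7-day window, so even with dosing stopped at season end the visit could fall within 5 days of the last dose.

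The second objection is that Section 7.2 sets a duty to report and does not promise a solicited contact on the last day. Other routes stay open: unscheduled visits (Section 2.1), the identification card with site telephone numbers (Section 7.1.1.4), the instruction to contact the site about significant events (Section 5.2.2.2), and reporting of related serious events at any time (Section 7.2.3.1). This is correct. The likely loss is mainly of minor events that nobody volunteers.

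Third, the days concerned carry little safety information. They are at most the last 5 of 14 days off drug, whereas the SLIT Report Card targets local reactions within 60 minutes of dosing. That also stands, and it limits the importance of the point.

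**Conclusion.** The mismatch is real and of low importance. A fully compliant call can come up to 5 days before the reporting period closes. The 5-day figure requires both a last dose on the day of Visit 8 and a call on the first permitted day. A call on the Day 14 target or later leaves no gap, nor does a last dose 5 or more days before Visit 8. The documents do not show how many calls would be early, so no expected loss is estimated. The same window applies to both blinded arms, and no between-arm bias or effect on power or the efficacy analysis is claimed. The change is worth making because it is cheap and makes the schedule deliver the follow-up that the protocol states.

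**What to change.** In the Section 6.0 flow chart, change the Telephone/Follow-up scheduling window from ± 5 days to +5 days, so that the call falls on Days 14 to 19 after Visit 8 or the discontinuation visit. The protocol already uses a forward-only window so that a fixed collection period is completed first. Footnote c of the flow chart reads: "Visit 3 should be scheduled on Day 28 (+7 days) to allow the subject to complete the SLIT Report Card for ~28 days".

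The cost is one flow-chart entry in an amendment, with no added contact. Sites lose the option of calling early, some calls come a few days later, and the window narrows from 11 days (Days 9 to 19) to 6 (Days 14 to 19), which leaves less room to reach families. Follow-up would still vary in length, but every subject who is reached in window would have at least the stated 14 days.
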